12.2.1 Dose modification guidelines for carfilzomib

In a case of study-related adverse event, the clinical investigator must assess its possible relationship to carfilzomib, lenalidomide and dexamethasone.

Local investigators can decide to not follow this dose modifications if they feel it is not in the best medical interest of the patient.

| Carfilzomib dose reduction guidelines for toxicity and dose modification | | | |
|---|--------------------------------|--------------------------------|--------------------------------|
| | 1 st dose reduction | 2 nd dose reduction | 3 rd dose reduction |
| 36 mg/m ² | 27 mg/m ² | 20 mg/m ² | 15 mg/m ² |

If a patient requires an interruption of carfilzomib of more than four weeks this study patient will be removed from study; all exceptions to this must be discussed with principal investigator. If the carfilzomib dose is reduced once, it will be continued for at least one cycle. In case this cycle is tolerated, the dose level prior to reduction may be resumed by the investigator's discretion. If carfilzomib is stopped permanently due to toxicity, all study medication will be stopped and the patient will proceed to end-of-study visit.

12.2.2 Carfilzomib dosing guidelines for hematologic toxicity

Hematologic toxicity

Recommended action

Thrombocytopenia

Platelets $\leq 30 \times 10^9/l$

If $10-30 \times 10^9/l$ without bleeding continue the same dose

If evidence of bleeding or platelets $< 10 \times 10^9/l$, withhold dose until platelets return to $\geq 10 \times 10^9/l$ and/or bleeding is controlled, then resume the same dose

For each subsequent drop
to $\leq 30 \times 10^9/l$

If $10-30 \times 10^9/l$ without bleeding continue at the same dose

If evidence of bleeding or platelets $< 10 \times 10^9/l$, withhold dose until platelets return to $\geq 10 \times 10^9/l$ and/or bleeding is controlled, then resume at 1 dose reduction.

Neutropenia

If $ANC \leq 0.75 \times 10^9/l$

If $ANC 0.5-0.75 \times 10^9/l$, continue at the same dose

If $ANC < 0.5 \times 10^9/l$, withhold dose until ANC returns to $\geq 0.5 \times 10^9/l$, then resume at the same dose.

For each subsequent drop to
 $\leq 0.75 \times 10^9/l$

If $ANC 0.5-0.75 \times 10^9/l$, continue at the same dose

If $ANC < 0.5 \times 10^9/l$, withhold dose until ANC returns to $\geq 0.5 \times 10^9/l$, then resume at 1 dose reduction

Neutropenic fever

If $ANC < 0.5 \times 10^9/l$, and single temperature $> 38.5^\circ C$ or temperature $> 38.0^\circ C$ more than one hour, withhold dose until ANC returns to baseline level, then resume at the same dose.

ANC = absolute neutrophil count.

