8. STUDY POPULATION

8.1 Inclusion criteria

Each patient must meet all the following inclusion criteria to be enrolled in the study:

1. At least 18 years of age, with at least 6 months expected survival.
2. Prior confirmed diagnosis of multiple myeloma (2014) (16).
3. Received standard first line treatment with at least a very good partial response (VGPR), according to IMWGs criteria . Standard first line treatment is defined as

VRD, VTD or VCD followed by ASCT with or without lenalidomide maintenance initiated (Patients where the monoclonal component or dFLC increases during the period from best response to screening can be included if there is no progressive disease.)

4. Patients must be carfilzomib naïve.
5. A positive PET-CT result from central reviewer in the screening period

6. Successful FISH evaluation performed with available results
7. Voluntary written consent must be given before performance of any study related procedure not part of standard medical care, with the understanding that the patient may withdraw consent at any time without prejudice to future medical care.
8. Females of childbearing potential (FCBPs) must have a confirmed negative serum pregnancy test within the 7 days prior to inclusion
9. FCBPs and male subjects who are sexually active with FCBP must agree to use highly effective concomitant methods of contraceptive during the study and for 30 days following the last study drug dose. Male subjects must use contraception and refrain from donating sperm for at least 90 days after the last dose of carfilzomib.
10. Eastern Cooperative Oncology Group (ECOG) performance status 0-2. In patients >75 years of age, performance status 0-1.
11. Patients must meet the following adequate organ and bone marrow function within 21 days prior to inclusion:
 - Absolute neutrophil count (ANC) $\geq 0,5 \times 10^9/L$ and platelet count $35 \times 10^9/L$. Platelet transfusions to help patients meet eligibility criteria are not allowed within 3 days before study enrollment. Granulocyte growth factors are allowed to meet the inclusion criteria.
12. Patient must be willing and able to adhere to the study schedule and other protocol requirements.

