12.2.3 Carfilzomib dosing guidelines for nonhematologic toxicity

| Nonhematological toxicity | Recommended action |
|---|--|
| Serum creatinine equal to or greater than 2 x baseline, or CrCl decreases to $\leq 50\%$ of baseline or need for dialysis | Withhold dose and continue monitoring the renal function If attributable to carfilzomib, resume when renal function has recovered to within 25% of baseline, start at 1 dose level reduction If not attributable to carfilzomib, dosing may be resumed at the discretion of the physician Patient will be withdrawn from study in case of permanent dialysis need |
| \geq grade 3 elevation in liver function tests | Withhold dose and resume at 1 dose reduction level when toxicity has recovered to baseline |
| Grade 3 infection | Withhold carfilzomib until infection resolves and resume at the same dose |
| Congestive heart disease | Any subject with symptoms of congestive heart failure, whether or not drug related, must have the dose held until return to baseline, after which treatment may continue at a reduced dose, or consider discontinuation of study protocol. If no recovery in 4 weeks, patient must be withdrawn. |

| | |
|--|--|
| LVEF: For resting LVEF < 40% or reduction of LVEF to < 55% from baseline, if the drop is greater than 20% from baseline | Withhold until LVEF returns to > 40% or, if held due to a drop to < 55%, to within 15% of baseline and resume at 1 dose reduction. |
| PRES: posterior reversible encephalopathy syndrome; headache, altered mental status, seizures, visual loss, hypertension | Stop carfilzomib and study treatment and the patient is withdrawn from study. If visual or neurological symptoms, neuroradiological imaging is recommended. |
| Thrombotic microangiopathy (TMA) | If suspected, hold carfilzomib and manage per standard of care, including plasma exchange as clinically appropriate. If TMA is confirmed and related to carfilzomib, permanently discontinue carfilzomib. If the diagnosis is excluded, carfilzomib can be restarted |
| Other grade 1 or 2 nonhematologic toxicity | Continue at the same dose |
| Any other drug-related nonhematologic toxicity ≥ grade 3 | If attributable to carfilzomib, withhold dose Resume at 1 dose reduction when toxicity has resolved to grade 2 or less or to baseline If tolerated, the reduced dose may be escalated to the previous dose at the discretion of the physician |

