13. SAFETY

Study investigators must follow the study protocol treatment and follow the dose reduction and adjustment guidelines in every study patient. Dose interruptions and modifications from other reasons can be performed at physician's discretion. Exceptional issues should be discussed with the principal investigator. Adverse event will be documented if observed, mentioned during open questioning, or when spontaneously reported.

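### Section 12.2.2 gives two different carfilzomib restart doses for a repeat neutropenia below 0.5 × 10⁹/l with fever, and does not say which applies

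*Protocol*

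**What the plan says.** The neutropenia part of the table in Protocol 12.2.2 is split by recurrence.

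- **First drop to ANC 0.75 × 10⁹/l or below:** carfilzomib continues at 0.5–0.75. Below 0.5 it is held until ANC is at least 0.5 and restarted unchanged.
- **Each subsequent drop to 0.75 or below:** the same, except that below 0.5 the instruction after recovery is "then resume at 1 dose reduction".
- **Neutropenic fever:** triggered by ANC below 0.5 plus a temperature criterion. The instruction is "withhold dose until ANC returns to baseline level, then resume at the same dose". It makes no distinction between a first and a later episode.

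The dose ladder in 12.2.1 runs 36, 27, 20, 15 mg/m². The same section says "Local investigators can decide to not follow this dose modifications" if they judge that following them is not in the patient's best medical interest. Section 13 (Safety) requires investigators to "follow the dose reduction and adjustment guidelines in every study patient", and adds that "Dose interruptions and modifications from other reasons can be performed at" the physician's discretion. In 12.2.3 the grade 3 infection row reads "Withhold carfilzomib until infection resolves and resume at the same dose", again without a split by recurrence.

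**The concern.** A patient who has already had one qualifying drop, and who then falls below 0.5 with fever, satisfies the subsequent-drop row and the fever row at once. The first calls for one dose level less and the second for no change. An investigator trying to follow the table cannot tell from it which dose to give.

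At stake is consistent dosing across the five participating centres and, to a small degree, patient safety. If the fever row is taken to govern, a recurrence complicated by fever restarts one level higher than an uncomplicated one.

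**Working it through.** No sample size or error rate is involved, so the check is to set the rows side by side for every case with ANC below 0.5.

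| Episode | Neutropenia rows | Fever row | Restart dose agrees? |
|---|---|---|---|
| First drop, no fever | same dose | not triggered | yes |
| First drop, fever | same dose | same dose | yes |
| Subsequent drop, no fever | one level lower | not triggered | yes |
| Subsequent drop, fever | one level lower | same dose | **no** |

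The conflict is confined to the last case.

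**Size of the step** (ladder in 12.2.1; fever row against subsequent-drop row):

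- From 36 mg/m²: 36 against 27, a difference of 36 − 27 = 9 mg/m² per infusion (9/36 = 25%).
- From 27 mg/m²: 27 against 20, a difference of 7 mg/m².
- From 20 mg/m²: 20 against 15, a difference of 5 mg/m².

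**Do the hold criteria also conflict?** One row releases at ANC 0.5 or above, the other at baseline level. Criterion 11 in 8.1 ("Patients must meet the following adequate organ and bone marrow function within 21 days prior to inclusion") sets an entry ANC of at least 0.5. If baseline means that entry count, a patient held to baseline has also reached 0.5. The fever row is then the stricter of two compatible criteria, and only the restart dose is in conflict.

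**Is there a precedence rule elsewhere?** None appears in 12.2.1, in 12.2.3 and the list after it of conditions that need no reduction, in 12.3.2 for lenalidomide, or in section 13.

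**What does the table's own pattern suggest?** The platelet rows of 12.2.2 place their complication, bleeding, inside the first/subsequent split: same dose the first time, one level lower on recurrence. Lenalidomide in 12.3.2 likewise steps down after each subsequent drop below its own threshold. The grade 3 infection row in 12.2.3 points the other way, since it restarts unchanged every time. The pattern leans towards a reduction on recurrence but does not settle the question.

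**The case against.** The strongest reply is that neutropenic fever is a separately named toxicity with a narrower trigger and its own release point, so the specific row should override the general one. The infection row in 12.2.3 fits that reading. But neither row contains the other. The fever row is narrower on temperature, and the subsequent-drop row is narrower on recurrence. Specificity therefore does not choose between them, and the protocol states no such convention. What stands is that the sponsor could equally remove the ambiguity by declaring that the fever row governs. Choosing the reduction is partly a clinical judgement, supported by the bleeding pattern.

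The second reply is that the column is headed as recommended action and 12.2.1 lets investigators depart from it, so doses could differ between sites even under a clear table. This stands as to consequence and is why the point is minor. A licence to depart from a guideline still does not say what the guideline is.

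Third, the table in 12.2.2 reached this review as flattened text. A merged cell that limited the fever row to first episodes would not be visible, so the printed page should be checked.

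A reader might also infer a material loss or excess of total carfilzomib, or an effect on PET-CT conversion. The documents support neither. The hold itself removes infusions, 12.2.1 and 12.2.2 do not say whether held doses are skipped or postponed, and a reduced dose may be raised again. The cumulative difference could be nil for an episode late in cycle 4. Only the one-level step per infusion follows from the text.

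**Conclusion.** The point holds as a minor inconsistency in a bedside dosing rule. A subsequent drop with ANC below 0.5 and fever has two restart doses one ladder step apart, 27 or 36 mg/m² for a patient on full dose, and no text decides between them.

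This rests on reading both rows literally and on the flattened table having lost no nesting. Few patients are likely to be affected, but that is a judgement: the documents give no frequency for recurrent febrile neutropenia. Three provisions soften the consequence: the investigator's discretion, the interruption of lenalidomide already at ANC below 1.0 × 10⁹/l (12.3.2), and the permitted therapeutic use of growth factors (12.6.2). No effect on the primary endpoint is claimed.

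**What to change.** Let the fever row alter only the hold criterion and take the restart dose from the neutropenia rows. For example: *hold carfilzomib until ANC is back at baseline and the fever has resolved; then restart unchanged if this is the patient's first drop to ANC ≤0.75 × 10⁹/l, or one dose level lower if it is a later drop to ≤0.75 with ANC <0.5.*

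The count must use the table's own threshold of 0.75. If the fever row counted only episodes below 0.5, a patient with a first drop to 0.6 and a febrile second drop to 0.4 would still be told to reduce by one row and to stay at the same dose by the other.

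Add a sentence that this rule also governs when a grade 3 infection (12.2.3) accompanies the repeat neutropenia; otherwise that row brings the overlap back. The condition that fever has resolved is an addition in line with the infection row and is not needed to remove the conflict.

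The cost is an amendment to one table row and one cross-reference, with no extra visits or procedures. The clinical downside is one dose level less carfilzomib in the few patients affected. It is bounded by 12.2.1: "If the carfilzomib dose is reduced once, it will be continued for at least one cycle", after which the previous level may be resumed at the investigator's discretion if that cycle was tolerated.

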12.2.3 Carfilzomib dosing guidelines for nonhematologic toxicity

| Nonhematological toxicity | Recommended action |
|---|--|
| Serum creatinine equal to or greater than 2 x baseline, or CrCl decreases to $\leq 50\%$ of baseline or need for dialysis | Withhold dose and continue monitoring the renal function If attributable to carfilzomib, resume when renal function has recovered to within 25% of baseline, start at 1 dose level reduction If not attributable to carfilzomib, dosing may be resumed at the discretion of the physician Patient will be withdrawn from study in case of permanent dialysis need |
| \geq grade 3 elevation in liver function tests | Withhold dose and resume at 1 dose reduction level when toxicity has recovered to baseline |
| Grade 3 infection | Withhold carfilzomib until infection resolves and resume at the same dose |
| Congestive heart disease | Any subject with symptoms of congestive heart failure, whether or not drug related, must have the dose held until return to baseline, after which treatment may continue at a reduced dose, or consider discontinuation of study protocol. If no recovery in 4 weeks, patient must be withdrawn. |

| | |
|--|--|
| LVEF: For resting LVEF < 40% or reduction of LVEF to < 55% from baseline, if the drop is greater than 20% from baseline | Withhold until LVEF returns to > 40% or, if held due to a drop to < 55%, to within 15% of baseline and resume at 1 dose reduction. |
| PRES: posterior reversible encephalopathy syndrome; headache, altered mental status, seizures, visual loss, hypertension | Stop carfilzomib and study treatment and the patient is withdrawn from study. If visual or neurological symptoms, neuroradiological imaging is recommended. |
| Thrombotic microangiopathy (TMA) | If suspected, hold carfilzomib and manage per standard of care, including plasma exchange as clinically appropriate. If TMA is confirmed and related to carfilzomib, permanently discontinue carfilzomib. If the diagnosis is excluded, carfilzomib can be restarted |
| Other grade 1 or 2 nonhematologic toxicity | Continue at the same dose |
| Any other drug-related nonhematologic toxicity ≥ grade 3 | If attributable to carfilzomib, withhold dose Resume at 1 dose reduction when toxicity has resolved to grade 2 or less or to baseline If tolerated, the reduced dose may be escalated to the previous dose at the discretion of the physician |

Conditions not requiring dose reduction of carfilzomib: Grade 3 nausea, vomiting or diarrhea, unless persisting more than 3 days with adequate treatment of antiemetics or antidiarrheal agents. Grade 3 dexamethasone-related hyperglycemia. Grade 3 fatigue, unless persisting for > 14 days. Alopecia.

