| SJS | stevens-johnson syndrome |
| SPMs | second primary malignancies |
| SUSAR | suspected unexpected severe adverse event |
| TEN | toxic epidermal necrolysis |

| | |
|------|---|
| TTNT | time to next treatment |
| VCD | bortezomib cyclophosphamide dexamethasone |
| VGPR | very good partial response |
| VRD | bortezomib lenalidomide dexamethasone |
| VTD | bortezomib thalidomide dexamethasone |
| VTE | deep vein thrombosis |

STUDY PROCEDURES

| | Screening (Day -28-0) | Day 1 Cycle 1 | Day 15 Cycle 1-4 | Day 1 Cycle 2-4 | Day 2, 8, 9, 15,16 Cycle 1-4 | Visit D1 C4D29 +/- 2 days | Visit D2 one month after D1 +/- 2 days | Every second months +/- 7 days | EOT at PD | Every 3m after PD until death |
|--|--------------------------|------------------|---------------------|--------------------|------------------------------------|---------------------------------|--|--|--------------|--|
| Medical/treatment history | X | | | | | | | | | |
| Complete physical examination, including height | X | | | | | | | | | |
| Targeted physical examination | | X | | X | X | X | X | X | X | |
| Vital Signs ^a | X | X | | X | X | X | | | | |
| Hematology ^b | X | X | X | X | | X | X | X | X | |
| Comprehensive blood chemistry panel ^c | X | X | | X | | X | X | X | X | |
| Evaluation of clonal disease ^d | X | X | | X | | X | X | X | X | |
| Safety assessment, AEs | X | X | | X | X | X | X | X | X | |
| Targeted neurologic evaluation | X | X | | X | X | X | X | X | X | |
| Quality of life evaluation | | X | X | X | | X | X | | X | |
| BM aspiration for MRD Euroflow | | X | | | | X | | | | |
| PET-CT | X | | | | | | X | | | |
| ECG | X | | | | | | | | | |
| ECHO cor, if clinically indicated | X | | | | | | | | | |
| Pregnancy test in fertile women | X | X | | X | | X | X | X | X | |
| Use of diuretics | X | X | | X | X | X | | | | |
| Overall survival | | X | | X | X | X | X | X | X | X |

^a Heart rate, blood pressure, temperature, weight

^b Neutrophils, hemoglobin, platelets

^c Hematology, SR, CRP, Potassium, Sodium, Total calcium, ionized calcium, magnesium, phosphate, creatinine, estimated GFR, ASAT, ALAT, gGT, ALP, LD Trop T, Pro-BNP, Bilirubin, Glucose, Albumin, Total protein, Uric acid

^d Serum and urine electrophoresis with immune fixation; serum free light chains; bone marrow aspirate/biopsy if CR/sCR is suspected from last visit

Introduction

| | |
|---|-----------|
| 1.1 Scientific background | 10 |
| 1.2 MRD measurement | 10 |
| 1. STUDY DRUGS..... | 11 |

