11. TREATMENT

12.1 Study Drug Administration Schedule

28-day cycle

| Cycles 1 | | | |
|-----------------|----------------------|--------------|--------------|
| Agent | Dose/day | Route | Days |
| Carfilzomib | 20 mg/m ² | IV | 1, 2 |
| | 36 mg/m ² | IV | 8, 9, 15, 16 |
| Lenalidomide | 25 mg | Oral | 1-21 |
| Dexamethasone | 40 mg | Oral | 1, 8, 15, 22 |

| Cycles 2-4 | | | |
|-------------------|----------------------|--------------|--------------------|
| Agent | Dose/day | Route | Days |
| Carfilzomib | 36 mg/m ² | IV | 1, 2, 8, 9, 15, 16 |
| Lenalidomide | 25 mg | Oral | 1-21 |
| Dexamethasone | 40 mg | Oral | 1, 8, 15, 22 |

During Cycles 1-4, administration of carfilzomib can be adjusted within the following window:

Day 1 -0/+2 days

Day 2 \pm 0

Day 8 -1/+1

Day 9 \pm 0

Day 15 -1/+1

Day 16 \pm 0

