13.4 Blood chemistry

Blood, bone marrow and urine samples will be sampled according to the flow chart.

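### Carfilzomib hold rules depend on laboratory values, but no scheduled test would detect a new fall in counts before the Day 8-9 doses or a new creatinine or liver-test rise before the Day 8-9 and Day 15-16 doses

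*Protocol*

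**What the plan says.** Section 12.1 gives carfilzomib on Days 1, 2, 8, 9, 15 and 16 of four 28-day cycles. The dose is 20 mg/m² on Days 1-2 of cycle 1 and 36 mg/m² on every later dosing day.

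The hold rules are these (counts in 10⁹/l):

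- Section 12.2.2, neutrophils below 0.5: "withhold dose until ANC returns to" at least 0.5.
- Section 12.2.2, platelets below 10, or bleeding: "withhold dose until platelets return to" at least 10 and/or the bleeding is controlled.
- Section 12.2.3, renal: "Serum creatinine equal to or greater than 2 x baseline, or CrCl decreases to" half of baseline or less, or need for dialysis.
- Section 12.2.3, liver: a "grade 3 elevation in liver function tests" or worse.

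Sampling times come from the flow chart under Study Procedures. Section 13.3 lists the hematology tests without time points, and section 13.4 refers back to the chart: "Blood, bone marrow and urine samples will be sampled according to the flow chart". During treatment the chart marks hematology on Day 1 and Day 15 of each cycle. It marks the row "Comprehensive blood chemistry panel", which holds creatinine, estimated GFR and transaminases, on Day 1 only. The column "Day 2, 8, 9, 15,16 Cycle 1-4" has examination, vital signs, adverse-event, neurologic, diuretic-use and survival checks, but neither hematology nor chemistry.

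**The concern.** A hold rule with a laboratory threshold works only if a result is available when the dose is given. On the scheduled tests alone, the Day 8-9 doses are decided on counts and chemistry from Day 1, and the Day 15-16 doses on chemistry from Day 1. A patient who is acceptable on Day 1 and crosses a threshold afterwards would be dosed without the crossing being known.

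The document gives reasons to care. Section 8.1 admits patients with neutrophils of 0.5, which is the hold threshold itself, and lists no renal or hepatic limit. Section 2.3 names grade 3-4 neutropenia and thrombocytopenia as the most common dose-limiting events with lenalidomide, and also reports liver-test abnormalities. In cycle 1, Day 8 is the first dose at 36 mg/m², after 20 mg/m² on Day 2.

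What is at stake is patient safety and even application of the hold rules across five centers. If extra testing is left to local habit, the same toxicity may lead to a hold at one site and a full dose at another.

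**Working it through.** The plan states no figure on this point, so there is none to reproduce. The check compares the dosing days (section 12.1) with the sampling days (flow chart).

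**Age of the latest scheduled result, nominal days**

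| Dosing days | Counts | Chemistry |
|---|---|---|
| 1, 2 | 0-1 day | 0-1 day |
| 8, 9 | 8 − 1 = 7; 9 − 1 = 8 days | 7-8 days |
| 15, 16 | 0-1 day | 15 − 1 = 14; 16 − 1 = 15 days |

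Section 12.1 says that "administration of carfilzomib can be adjusted within the following window": one day either way for Days 8 and 15. If those windows are counted from the actual Day 1, and Days 9 and 16 follow Days 8 and 15 directly (an assumption), the ages run 6-9 days for Days 8-9 and 13-16 days for Days 15-16.

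**Doses**

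- Planned doses: 6 × 4 = 24.
- Counts not from the same or previous day: Days 8-9, 2 × 4 = 8 of 24 (33.3%).
- Chemistry not from the same or previous day: Days 8, 9, 15 and 16, 4 × 4 = 16 of 24 (66.7%).

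**Share of planned carfilzomib**

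- Cycle 1: 2 × 20 + 4 × 36 = 184 mg/m².
- Cycles 2-4: 3 × 6 × 36 = 648 mg/m².
- Total: 184 + 648 = 832 mg/m².
- Days 8-9: 2 × 36 × 4 = 288; 288/832 = 34.6%.
- Days 8, 9, 15 and 16: 4 × 36 × 4 = 576; 576/832 = 69.2%.
- Dose step at Day 8 of cycle 1: 36/20 = 1.8.

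**Patients already covered**

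- A patient who meets a hold threshold on Day 1 stays on hold until recovery is shown, so a repeat test is implied before the next dose.
- Section 12.3.2 asks for weekly blood counts once neutrophils fall below 1.0 or platelets below 30 and lenalidomide is interrupted. If that is seen on Day 1, a count is due at about Day 8.
- For counts, the clearly uncovered cases are therefore Day 1 neutrophils of at least 1.0 falling below 0.5, a fall of more than (1.0 − 0.5)/1.0 = 50%, or Day 1 platelets of at least 30 falling below 10, a fall of more than (30 − 10)/30 = 66.7%.
- For chemistry, section 12.2.3 requires continued renal monitoring only after the rise has been found. No conditional weekly test exists for creatinine or liver tests.

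The 8 and 16 doses are therefore upper bounds. The document gives no rate for new falls or rises within a cycle, so the number of patients affected cannot be estimated.

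**The case against.** The strongest reply is that nothing here is stated wrongly. Sections 12.2.2 and 12.2.3 are guidelines that recommend an action when a toxicity is present, and nowhere does the protocol require a same-day or previous-day result before each infusion. A flow chart sets the minimum and does not forbid more. Section 14.9 anticipates safety assessments beyond those required, section 2.3 advises renal monitoring in renal impairment, and section 13 (Safety) lets physicians interrupt dosing at discretion. Examination, vital signs and adverse-event review take place on every dosing day. The plan also tolerates low counts on purpose: dosing continues at neutrophils of 0.5-0.75 and at platelets of 10-30 without bleeding. The 1.8-fold step occurs in cycle 1 only, and section 7.4 regards 36 mg/m² as well tolerated in newly diagnosed patients.

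Much of this stands. It makes the point one of monitoring frequency and keeps it minor. It does not close the gap: none of those sections sets a Day 8 draw or a Day 15 chemistry test, and a bedside examination can reveal fever or bleeding but not a neutrophil count, creatinine or transaminase.

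A reader might infer that the Day 8-9 doses have no laboratory result at all, or that no scheduled test could ever trigger a hold there. The documents do not support that. Day 1 results exist, holds that begin on Day 1 carry forward, and the conditional weekly count covers some patients. One caveat applies to the last: section 12.3.2 speaks of counts that fall, so whether it reaches a patient who enters cycle 1 with neutrophils already between 0.5 and 1.0 is open to reading.

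**Conclusion.** The point holds for new abnormalities. A first fall in neutrophils or platelets between Day 1 and Day 8, or a first rise in creatinine or liver tests after Day 1, would not be detected by any scheduled test before the Day 8-9 doses (counts and chemistry) or the Day 15-16 doses (chemistry). At most 8 of 24 doses for counts and 16 of 24 for chemistry are affected, assuming full planned dosing on nominal days. The chemistry gap is the wider one, because it is longer and has no conditional rule behind it.

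A reader might take the dose shares as a measure of risk. They describe how old the results are; they say nothing about how often a threshold is crossed. This is a minor, cheap safety improvement, and it bears on neither the sample size nor the primary analysis method.

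**What to change.** Change the flow chart in two places:

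1. Add creatinine and liver tests to the Day 15 sample already drawn in each cycle.
2. Add neutrophils, platelets, creatinine and liver tests at the Day 8 infusion visit of each cycle.

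Both sets of results should be reviewed before dosing. Days 9 and 16 then rely on the previous day's result, and all 24 doses have counts and chemistry from the same or previous day.

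The cost is at most 4 × 50 = 200 extra routine samples on Day 8, and creatinine and liver tests on at most 4 × 50 = 200 existing Day 15 samples. No extra visits are needed, though patients will sometimes wait for results. More testing will also produce some more holds. Under section 12.2.1 an interruption of more than four weeks means removal unless an exception is agreed. If the later PET-CT is then missing, the worst-case rule in section 16.7 would count the patient as not converted. The sponsor should accept that consequence knowingly; it is no reason to leave the tests out.
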